1.6 Potential Benefits to Participants

Since the study participants will be required to collect repeated blood and urine samples and stop their study treatment for 3 months during the follow up, this study has to be considered as a study without a direct therapeutic benefit resulting from their participation in this study. However subjects enrolled in this study should be improved by Smecta® for their symptoms related to their chronic functional diarrhoea during the study treatment period.

1.7 Rationale for the Study

The recent ICH guideline on elemental impurities (ICH Q3D, step 4, 2014) imposes to perform a risk assessment on medicinal products containing elemental impurities. These elemental impurities consist in particular in cadmium, lead, arsenic, mercury, cobalt, vanadium, nickel, that may be present in natural constituents of mineral origins such as diosmectite extracted from a quarry.

These elemental impurities have been categorised in ICH Q3D guidelines into 3 classes (refer to Attachment #5_Section 15.5) based on their toxicity (based on a permitted daily exposure (PDE)) and likelihood of occurrence in the drug product.

For other elements such as aluminium, manganese or zinc no limiting PDE has been established yet.

Lead has been identified as the major elemental impurity in Smecta®; indeed, in case of chronic diarrhoea posology i.e. 3 sachets of diosmectite (Smecta®) or 9 g per day, the lead intake could be a total amount of approximately 46.35 $\mu g/day$. This amount exceed the amount allowed by the new upcoming ICH Q3D guideline which comes in force for existing marketed drug in December 2017, and that will limit the lead ingestion PDE to 5 $\mu g/day$.

The amount of other Class I elemental impurities contained in 3 sachets of diosmectite (Smecta®) such as arsenic and barium are approximately 4.23 $\mu g/day$ and 1395 $\mu g/day$ respectively and thus below their respective new PDE (15 $\mu g/day$ for arsenic and 1460 $\mu g/day$ for barium).

In vitro studies aiming at reproducing the gastrointestinal environment, have evidenced lead and other elements delivery from clay in acid pH, and reintegration of the elements in the clay sheets in basic pH environment. Experimental studies in animal models for assessing the bioavailability and absorption of elemental impurities have not been evaluated as predictive of human exposure.

However, how much of this lead could be bioavailable for potential stomach and intestine absorption in adult patients after chronic oral ingestion of Smecta® is unknown as well as the absorption of these elemental impurities.

From more than 40 years of sales of Smecta®, no adverse events potentially related to elemental impurities, particularly saturnism and/or chronic lead intoxication symptoms have been reported to Ipsen or to Health Authorities. In addition, no signal within the Ipsen Pharmacovigilance Safety Data Base, and notably in targeted body systems (such as nervous system, blood and lymphatic, renal and urinary), has been detected.

Furthermore, declaration of lead intoxication is mandatory in France. Between 1995 and 2014, neither lead intoxication, nor blood lead level $> 100 \mu g/l$ have been reported in children taking Smecta® to the SNSPE (Système National de Surveillance de Plombémie chez l'Enfant).

However, regarding the new ICHQ3D guidelines, Smecta® does not comply with the new requirements. Therefore, the MAH considered that in order to perform an appropriate risk assessment of elemental impurities contained in Smecta®, including lead as primary elemental constituent, clinical data need to be generated in humans after chronic administration of Smecta®.

Lead is a common element found in low concentration in the Earth's crust. It is widely used in industry, particularly in products such as construction materials, paint, batteries and piping. Lead causes health problems such as toxicity of the liver, kidneys, hematopoietic system and nervous system. During the 70's and 80's, concern over lead related health problems led to the introduction of unleaded gasoline and the banning of lead based paint (for review see Kim et al. 2015). After lead enters the body, it can transit along several pathways depending on its source (organic or inorganic). The fraction of lead that is absorbed depend mainly on the physical and chemical form. Other important factors are subject's specific such as age, gender, smoking and nutritional status. The half-life of lead in the blood compartment is about 40 days in adults (99% of circulating lead is contained in the erythrocytes, Rabinowitz, 1991). The half-life of lead in blood of children and in pregnant women is reported to be longer due to bone remodelling. Residence time in other organs such as bone is much longer and ranges from 10 to 30 years. Whole blood and serum/plasma have been used as biological fluid used for the assessment of lead exposure both for screening, bio-monitoring and diagnostic purposes (Barbosa F et al. 2005, Falq et al. 2011).

Blood lead level (BLL) from whole blood is the main biomarker used to monitor exposure and has been widely used in numerous epidemiological studies. BLL is a balance between recent absorption of lead and a removal of lead stored in the body, especially in bone (Christoffersson et al., 1986; Nilsson et al., 1991) and is representative of the internal dose of lead in the organism when the exposure is stable (Barbosa et al., 2005). Plasma lead level could be a better biomarker, especially at high exposure (workers for example) (Rentschler and al, 2012 – Bergdhal and al, 1997). Reference ranges for estimation of a baseline of lead level in European Western countries are available for blood (Falq and al, 2011). Estimation of blood lead levels have been considered for the current study as the primary endpoint. In addition, it is proposed to biobank samples for potential assessment of lead levels in plasma.

The intestinal microbiota (containing about 90% of the body microorganisms) contributes to intestinal homeostasis through direct regulation of the development of the intestinal mucosa and maturation of the immune system. Therefore, the intestinal microbiota can be perceived as an integral component of the host's physiology.

An increasing number of studies emphasizes the diverse roles of the intestinal microbiota. These roles are often associated with beneficial physiological effects for the host, reflecting a symbiotic and beneficial crosstalk between cells of the intestinal epithelium and the resident microbiota. However, the cellular and molecular mechanisms developed by the microbiota in order to influence the host's intestinal cell responses remain poorly understood.

The understanding of the complex host-microbiota relationship and the possibility to modulate these interactions is of key importance for human health. Our knowledge on the various contributions of the microbiota to health is still in its infancy and the underlying cellular and molecular mechanisms of its interplay with the host intestinal cells remain poorly understood (de Wouters et al., 2014).

We would like to take the opportunity of this study to explore the potential effect of Smecta® on the microbiota by collecting selected faecal samples at various time point before, during and after the chronic administration of Smecta®.

2 STUDY OBJECTIVES

2.1 Primary Objective

To assess the concentration of lead in blood, one of the Class I elemental impurities defined by ICH Q3D guidelines, after chronic administration of Smecta® in subjects with chronic functional diarrhoea.

2.2 Secondary Objectives

- To assess blood concentration of other Class I and IIa elemental impurities of interest (i.e. arsenic, cadmium, mercury, cobalt, vanadium, nickel and barium) and of aluminium after chronic administration of Smecta® in subjects with chronic functional diarrhoea;
- To assess urinary lead levels and urinary levels of other selected Class I and IIa elemental impurities of interest (i.e. arsenic, cadmium, mercury, cobalt, vanadium, nickel and barium), and aluminium after chronic administration of Smecta®;
- To further assess the safety and tolerance of Smecta® after chronic administration.

2.3 Exploratory Objectives

- An ancillary study will be conducted during this study to assess the bowel microbiote composition, stools consistency and frequency after chronic administration of Smecta® in subjects with chronic functional diarrhoea.
- Additional blood samples will be biobanked in order to further potentially assay other elemental impurities levels (see Attachment #5 Section 15.5);
- Plasma samples will be biobanked in order to further potentially assay lead in plasma.

3 INVESTIGATIONAL PLAN

3.1 Overall Study Design

This is a prospective, open-label, non-comparative, multi-centre, international, without direct individual benefit study, assessing the potential absorption of elemental impurities after chronic administration of Smecta® in subjects with chronic functional diarrhoea. It is intended that a total of 35 subjects will be enrolled (i.e. assigned to a treatment, please see section 4.1) to ensure that at least 29 subjects will complete the study. It is planned to have at least 40% of each gender in the entire study.

After a screening period of up to 6 weeks including a baseline assessment, each subject will be dosed with Smecta® TID over 5 weeks (Day 1 to Day 35) and then continue to be monitored over a post-treatment follow-up period of 3 months until end-of-study visit (see Figure 1). Blood samples, urine collections and faecessampling will be obtained at screening phase and baseline visit, over the treatment period and then during follow-up period. Potential adverse events will be collected and monitored throughout the study.

No formal interim analysis is planned during the study. However, BLL obtained on screening and baseline (prior the first intake of Investigational Medicine Product (IMP)) and during the study will be analysed and reviewed on an ongoing basis by the Sponsor for potential study adjustments (e.g.: confirm assumptions for sample size calculation).

[figure not shown]

Figure 1 Study Design and Visits

3.2 Primary and Secondary Endpoints and Evaluations

Concentration of lead, other elemental impurities and other endpoints assessed in this study are further described below.

3.2.1 Pharmacokinetics of Lead, other Impurities Endpoints and Evaluations Methods

Primary Endpoints:

Changes in BLL from baseline during treatment and post-treatment follow-up period. PK parameters of lead may be calculated if feasible.

Secondary endpoints:

- Change from baseline of concentrations of other selected Class I elemental impurities (i.e. arsenic, barium) and Class IIa elemental impurities (i.e.: cadmium, mercury, cobalt, vanadium, nickel) and aluminium in blood during treatment and post-treatment follow-up
 - PK parameters of selected Class I and Class IIa impurities may be calculated if feasible.
- Change from baseline of urinary concentrations of selected Class I and IIa elemental impurities (arsenic, barium, cadmium, mercury, cobalt, vanadium, nickel) and aluminium in urine at the end of Smecta® administration and during follow-up period.

3.2.2 Exploratory Endpoints

3.2.2.1 Microbiote assessment

Microbiote characteristics will be evaluated during Smecta® treatment and follow up and compared to baseline.

The method of samples and dosing will be detailed in a separated technical document developed in collaboration with Institut National de la Recherche Agronomique (INRA) – Jouy-en-Josas, France.

Consistency of stools (recorded and rated according to Bristol scale) (See Attachment #7_Section 15.7) and frequency will be assessed over 24h by the subject as described in the Study Schedule (See Attachment #1 Section 15.1).

3.2.2.2 Biobank

Blood and urine samples will be stored for potential further dosages of other elemental impurities as lithium (Li), antimony (Sb), molybdenium (Mo), copper (Cu), Tin (Sn) and chromium (Cr).

Plasma samples will be biobanked in order to further potentially assay lead in plasma. If feasible, PK modelling of lead (and potentially other elemental impurities levels) may be performed.

3.2.3 Safety Endpoints and Evaluations

Safety Endpoints will be assessed as described in the Schedule of events (see in Attachment #1_Section 15.1):

- o physical examination, vital signs, ECG,
- o clinical laboratory blood tests (see in Attachment #2 Section 15.2),
- o Adverse Events and Treatment Emergent Adverse Events (TEAE).

To note: During the study additional assessments may be performed at the discretion of the Investigator in case of adverse events.

3.3 Subjects Managements

3.3.1 Study Visits and Procedures

Study visits and procedures are described in the Study Schedule of Events (see Attachment #1_Section 15.1).

It is planned that subjects will be resident in the Clinical Research Unit (CRU) at particular study visits, mainly during 24-hour urine collection. Otherwise, subjects will self-administer and come to the CRU at regular interval for drug supply, blood and urine collections as well

as the review of adverse event as described below in this section and in the schedule of events (see Attachment #1 Section 15.1).

Compliance to diosmectite (Smecta®) intake will be monitored through the use of subject diary.

3.3.1.1 Screening Period

The subjects will attend the CRU (Visit 1) to enter the screening period within 21 to 42 days prior to dosing Visit 2.

After a subject has been checked for pre selection criteria, has received complete explanations and response(s) to his/her potential questions about the study by the Investigator (or designee) and has been given reasonable time to think about it, a signed and dated informed consent form will be obtained prior to any study procedures.

Once informed consent is obtained, subjects will be allocated a study-specific subject number which must comply with formatting specifications provided by the Sponsor.

Demographic data will be collected including race, smoking status, alcohol consumption, and dietary habits.

The screening tests and assessments will then be performed to check compliance with Inclusion/Exclusion criteria and study restrictions. The results must be obtained and confirm subject's eligibility prior to dosing on Visit 2 at Day 1.

3.3.1.2 Baseline

The subjects will come back for admission to the CRU (Visit 2), 3 to 6 weeks later at the latest on Day -1 in the morning, at the discretion of the Investigator, to be resident in the CRU for obtaining a 24-hour urine collection as well as stool sample(s) for baseline evaluation. Based on Investigator judgement or if required locally, some of the screening assessments may be redone to confirm that subjects are still compliant with the Inclusion/Exclusion criteria and study restrictions.

3.3.1.3 Treatment Period

The treatment period will occur from Day 1 (first intake in the morning) to Day 35 (last intake in the evening) and subjects will be required to attend the CRU on several occasions during the treatment period:

- Day 1 (Visit 2): The subjects will be dosed within the unit with Smecta® at breakfast, lunch and dinner time, PK samples will be collected as described in the Schedule of events (see Attachment #1_Section 15.1) and the subject will leave the unit on Day 2 after PK sampling and Smecta® administration in the morning. Subjects will receive a box containing Smecta® treatment for a bit more than 2 weeks (20 days) as well as a diary to record the drug administration and consistency and frequency of stools at the day before the Day 8 visit.
- Out-patient visits (Visits 3 to 6): the subjects will be required to come back to the CRU for out-patient visits on Days 8, 15, 22 and 29 for blood sampling for impurities dosing and the review of adverse events and concomitant medication. One day before Day 8, subject will need to complete the diary with assessment of consistency and frequency of stools using the Bristol scale. During those visits, stools will be collected only on Day 8. At Day 22 the subjects will receive a second box containing Smecta® treatment for the last 2 weeks.
- Days 35-36 (Visit 7): Subjects will come back to the CRU in the morning of Day 35 (or the evening before for convenience) in order to start the process to collect urine samples, blood and stools sampling. They will be dosed with Smecta® at breakfast,

lunch and dinner. They will leave the unit in the morning of Day 36 after the completion of the 24-hour urine collection and PK sample in the morning.

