	 impurities (i.e. arsenic, barium) and Class IIa elemental impurities (i.e.: cadmium, mercury, cobalt, vanadium, nickel) and aluminium in blood during treatment and post-treatment follow-up period. Change from baseline of urinary concentrations of selected Class I and IIa elemental impurities (arsenic, barium, cadmium, mercury, cobalt, vanadium, nickel) and aluminium in urine at the end of Smecta® administration and during follow-up period. Safety Endpoints: physical examination, vital signs, ECG, standard clinical laboratory tests, adverse events and Treatment Emergent Adverse Events (TEAE) additional medical monitoring visit at the discretion of the Investigator and in case of adverse reactions.
	Exploratory endpoints:
	Change from baseline of the microbiote characteristics during Smecta® treatment and follow up.
	• Change from baseline of consistency of stools (as rated according to Bristol scale over 24h by the subject) and frequency at different study visits.
	• Change from baseline of blood and urine dosages of other elemental impurities as lithium (Li), antimony (Sb), molybdenium (Mo), copper (Cu), Tin (Sn) and chromium (Cr) at the end of Smecta® administration and during follow-up period.
	Change from baseline of plasma concentration of lead at the end of Smecta® administration and during follow-up period
Study Design	Prospective, open label, non-comparative study with treatment of Diosmectite (Smecta®, 3g) TID over 5 weeks.
Number of Subjects	A total of 35 subjects will be enrolled in order to ensure at least 29 subjects completing the study. It is planned to enrol a minimum of 40% of each gender, with gender distributed approximately equally between sites (e.g. no site with less than 35% of one gender).
Treatment: route, strength,	Diosmectite (Smecta® 3g/sachet, powder for oral suspension.
regimen	Three sachets per day (TID), morning, noon, and evening.
	For the purpose of this study, Smecta® should be taken fasting and at least one hour before meal, except for breakfast at least ½ hour before.
Reference/Control Treatment: route, strength, regimen	NA
Drug administration	Smecta® orange/vanilla 3g, sachet to be put in suspension in a glass of water.
Main Inclusion/Exclusion Criteria	- Male or female subjects, between 18 and 60 years old inclusive, BMI between 19 and 32 kg/m² inclusive (minimum body weight of 50 kg at screening).

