5.1.2 Study Drug Administration

The Investigator, or designee, will only dose and allocate Smecta® treatment to subjects enrolled in this study.

Two kits of Smecta® will be prepared and provided to subject(s) according to the predetermined dosing schedule agreed upfront with the Sponsor or designee; each kit consisting of one box, containing 60 sachets of Smecta® covering the administration for 20 days.

Each subject will be instructed to ingest Smecta® at three occasions, in the morning, at noon and in the evening, and every day until the Day 35 visit included. In order to standardize the conditions of administration of Smecta® and potentially limit the variability and increase bioavailability of lead all along the trial, Smecta® should be taken in fasting and at least one hour before meal, except for breakfast at least 30 minutes before.

The actual time of dosing of all Smecta® ingestions will be recorded by the subject on his/her own Diary as well as the start and ending time of the meals, and reported by the site in the eCRF, or will be recorded by the site when applicable in the eCRF.

Subjects will be instructed to contact the Investigator as soon as possible if he/she has a complaint or problem with the study drug so that the situation can be assessed.

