6 STUDY RESTRICTIONS

6.1 Study Drug Administration

The content of sachet should be reconstituted with water (approximately 200 ml), just before ingestion.

The regimen of intake is three times per day (TID) in fasting state, with consequently the following timings:

- at wake up time, at least 30 minutes before breakfast
- in the morning, 1 hour before lunch time
- in the late afternoon, 1 hour before dinner time

Example: if breakfast at 7:30, lunch at 12:30 and dinner at 19:30,

Smecta® intake should occur:

- at wake up time and before 7:00
- in the morning at 11:30
- in the late afternoon at 18:30

If a dose administration is missed, subject is instructed to ingest the missing dose together with the next dosing occasion. If no meal at a given day is taken (e.g. breakfast), Smecta® should be taken in fasting state anyway and at three occasions (see Section 5.1.2).

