7.3.1 Sampling Schedule

Urine collections (as 24-hour collection) and Blood samples for the measurement of elemental impurities will be collected as described in the Schedule of events (see Attachment #1_Section 15.1).

During the outpatient visits, blood samples will be collected pre-dose of any of the 3 dosing occasions of that day.

Taken into account the time window flexibility during the Day 35, the 24-hour urine collection should be done whilst subject is still under study treatment (e.g.: if subject performs the Day 35 at Day 36, Smecta® will be given until the evening of Day 36, or alternatively if subject comes at Day 34, the last Smecta® intake will be done at Day 34 evening).

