7.6.2 Compliance to Timing of Procedures

The specifications in this protocol for the timings and dates of primary tests are given as targets, to be achieved within reasonable limits. The scheduled time points may be subject to minor deviations within the allowed time windows specified in the Study Schedule of Events (see Section 15.1); however, the actual time must always be correctly recorded in the eCRF and other relevant source documents. Any excursion outside of these allowed time windows might be regarded as protocol violation.

Any major modification that might affect the conduct of the study, subject safety, and/or data integrity will be detailed in a protocol amendment.

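### The first 60-sachet box runs out before a Visit 5 held on Day 23, so an adherent late attender misses 2–5 doses (6–8 if the box also covers Day 1) before that blood lead sample

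*Protocol*

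**What the plan says.** The regimen is "Three sachets per day (TID), morning, noon, and evening" (Protocol synopsis), from Day 1 morning to Day 35 evening (Protocol 3.3.1.3).

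Protocol 5.1.2 provides two kits per subject, "each kit consisting of one box, containing 60 sachets of Smecta® covering the administration for 20 days". Protocol 3.3.1.3 gives the first at Visit 2: "Subjects will receive a box containing Smecta® treatment for a bit more than 2 weeks (20 days". The second comes at Visit 5: "At Day 22 the subjects will receive a second box containing Smecta® treatment for the last 2 weeks".

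The schedule of events (Protocol Attachment 1) gives Visit 5 a window of ±1 day. Protocol 7.6.2 treats this as permitted: "The scheduled time points may be subject to minor deviations within the allowed time windows specified in the Study Schedule of Events".

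On sampling, Protocol 7.3.1 says: "During the outpatient visits, blood samples will be collected pre-dose of any of the 3 dosing occasions of that day". On missed doses, Protocol 6.1 says: "If a dose administration is missed, subject is instructed to ingest the missing dose together with the next dosing occasion".

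Subjects are dosed in the unit on Day 1 and on the morning of Day 2. Neither document says whether those four doses come from the first box. Neither describes a bridging supply.

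**The concern.** The hand-out dates do not sustain the stated regimen across the permitted visit window. Even a box first opened at Day 2 noon is finished before Day 23. The subject who runs out has broken no rule; the supply plan causes the gap.

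Change in blood lead during treatment is the primary endpoint, and Visit 5 is one of its time points. Because the sample is taken before dosing, and the new box arrives only at that visit, the make-up rule cannot act before the sample. The error is towards lower exposure. The protocol otherwise aims the other way: it selects a batch at the maximal lead level (5.1.1) and fasting intake to raise lead bioavailability (3.5, 5.1.2).

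**Working it through.** **Inputs.** 60 sachets per box and two boxes (Protocol 5.1.2); three sachets per day (synopsis); Visit 5 on Day 22 ±1 (Attachment 1); pre-dose sample at any of the three occasions (7.3.1); blood half-life about 40 days (1.7); intake times 7:00, 11:30 and 18:30 (example in 6.1). The first dose taken from the box is not stated, so three cases are run: Day 1 morning, Day 2 morning and Day 2 noon.

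**The plan's own figure.** 60 / 3 = 20 days, as stated. Total supply is sufficient: 2 × 60 = 120 sachets against 35 × 3 = 105, or 108 if Visit 7 falls on Day 36. Only the timing is at issue.

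**Last dose from the first box.** Sixty slots from each start end on:
- Day 1 morning start: Day 20 evening
- Day 2 morning start: Day 21 evening
- Day 2 noon start: Day 22 morning

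**Doses missed before the Visit 5 sample** (visit before the morning / noon / evening dose):

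| Box starts | Visit on Day 21 | Visit on Day 22 | Visit on Day 23 |
|---|---|---|---|
| Day 2 noon | 0 / 0 / 0 | 0 / 0 / 1 | 2 / 3 / 4 |
| Day 2 morning | 0 / 0 / 0 | 0 / 1 / 2 | 3 / 4 / 5 |
| Day 1 morning | 0 / 1 / 2 | 3 / 4 / 5 | 6 / 7 / 8 |

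**Effect on the Smecta-related part of blood lead.** Assume one compartment and the same amount absorbed per dose. The level at the sample is proportional to the sum, over doses taken, of exp(−ln 2 × age / 40), with age in days. Two comparisons are useful: full dosing up to the same Day 23 sample, and an on-time Day 22 sample in the same slot. An on-time Day 22 sample follows 63 / 64 / 65 scheduled doses. A Day 23 subject has had 64 doses (Day 2 noon start), 63 (Day 2 morning) or 60 (Day 1).

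| Box starts, visit on Day 23 | Against full dosing to Day 23 | Against on-time Day 22 |
|---|---|---|
| Day 2 noon | −3.6 / −5.4 / −7.0% | +0.2 / −1.7 / −3.5% |
| Day 2 morning | −5.4 / −7.1 / −8.8% | −1.7 / −3.6 / −5.3% |
| Day 1 morning | −10.7 / −12.4 / −13.9% | −7.3 / −9.0 / −10.7% |

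For a Day 1 start and an on-time Day 22 visit, the shortfall is 5.6 / 7.4 / 9.1%.

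**Sensitivity to half-life (20 to 60 days), against full dosing to Day 23.** Day 2 noon start: 3.4–8.3%. Day 1 start: 10.2–16.2%.

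**Scale in µg/l.** The documents do not give the rise, so these values are illustrations. For rises of 1, 5 and 18.6 µg/l (the last is the plan's margin), a 7.0% shortfall is 0.07, 0.35 and 1.3 µg/l, and a 13.9% shortfall is 0.14, 0.7 and 2.6 µg/l.

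**Check of the remedy.** Sachets left from the first box at Visit 4 (pre-morning to pre-evening):

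| Box starts | Day 14 | Day 15 | Day 16 |
|---|---|---|---|
| Day 2 noon | 25–23 | 22–20 | 19–17 |
| Day 2 morning | 24–22 | 21–19 | 18–16 |
| Day 1 morning | 21–19 | 18–16 | 15–13 |

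At least 13 remain in every case.

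**The case against.** **Comparator.** The SAP (3.2.2.1) summarises changes by time point, so a Day 23 sample would presumably be reported under Day 22. Against an on-time Day 22 sample the loss for Day 2 starts is at most about 5%. A permitted Day 21 visit with full supply is already about 3.9% below Day 22. This stands: for Day 2 starts, the effect is of the order the window already accepts. Only a Day 1 start is clearly larger.

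**Which start is meant.** The subject is dosed in the unit, leaves after the Day 2 morning dose and takes the box home. Twenty days from Day 2 ends on Day 21, and the last two weeks are Days 22–35, so the wording fits a Day 2 morning start best. This also stands, although the text does not settle it. A reader might take eight missed doses as the expected gap. That needs a Day 1 start together with a pre-evening visit on Day 23.

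**Handled elsewhere.** Protocol 5.1.2 mentions a dosing schedule agreed with the sponsor and tells subjects to report problems with the study drug. Sites may also book Visit 5 on Day 21 or 22. None of this shows a bridging supply or an earlier hand-out, and a Day 23 visit remains permitted.

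**Make-up intakes.** A reader might infer that the make-up rule orders 9–27 g at one intake after a Day 23 visit. The rule speaks of one missing dose taken at the next occasion, and does not clearly require a run of missed doses to be stacked.

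**Weight.** Visit 5 is one of 21 post-baseline blood samples, and the SAP (3.1.6) plans no significance testing. The share of Day 23 attenders is unknown, so the effect on the reported mean is smaller than the per-subject figures. The assumed assay CV of 15% is about 4.7 µg/l at 31.4 µg/l. Every administration is listed (SAP 3.2.9), so a gap would be visible, although the compliance category would not flag it: eight doses missed and not made up give 97 / 105 = 92.4%, inside the 80–120% band.

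**Conclusion.** The point holds as a minor one. That the box is empty before a Day 23 visit follows from the protocol's own numbers under all three start points, for a subject who has taken every dose; earlier missed doses would stretch the box. The gap before the sample is 2–5 doses for Day 2 starts and 6–8 for a Day 1 start. Only a Day 1 start gives a gap of 3–5 doses at an on-time visit; for Day 2 starts it is 0–2.

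The percentage effects rest on the 40-day half-life, one compartment and constant absorption. They apply to the Smecta-related part of blood lead, not to its total.

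A reader might look for a ceiling on the effect on total blood lead. The documents do not support one, because the rise is unknown. With a 20-day half-life, a Day 1 start and a rise of 18.6 µg/l, the shortfall is 16.2% × 18.6 = 3.0 µg/l, or 6.0% of 50 µg/l; a larger rise would give more. Nor do the documents support reading this as a threat to the primary result. The clear effect is limited to late attenders at one time point and is unlikely to change the conclusion.

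**What to change.** In Protocol 3.3.1.3, hand out the second box at Visit 4 (Day 15 ±1) instead of Day 22. With 13–25 sachets of the first box still in hand, no gap can arise at Visit 5 under any start point. Optionally, state in 5.1.2 whether the unit doses on Day 1 and Day 2 come from the first box, and in 6.1 the maximum number of sachets at one intake.

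The cost is one dispensing date moved a week earlier, to a visit subjects already attend. The same 120 sachets are used, with no added visit, data or analysis.
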